# 2 INTRODUCTION

## 2.1 Trial Rationale

This placebo-controlled, double-blind trial is designed to assess the efficacy, safety, and tolerability profile of CVL-865 as adjunctive treatment in subjects with drug-resistant focal onset seizures.

The broad therapeutic use of nonselective benzodiazepines (BZDs) in multiple indications clearly supports the therapeutic potential of  $\gamma$ -aminobutyric acid type A (GABAA) positive allosteric modulators (PAMs) with the potential to offer efficacy with fewer side effects.

A double-blind, placebo-controlled trial is an appropriate design in which to assess initial efficacy with CVL-865. This proof-of-concept trial will assess whether CVL-865 demonstrates efficacy compared with placebo, as measured by a decrease in seizure frequency in subjects with a diagnosis of epilepsy with drug-resistant focal onset seizures.

## 2.2 Background

Epilepsy is the most common serious neurological condition in the world affecting approximately 60 million people worldwide. In the United States (US), more than 3 million people have been diagnosed with epilepsy or have experienced an unprovoked seizure. Approximately 20% to 30% of patients with focal onset seizures have seizures that are refractory to currently available anti-epileptic drugs (AEDs). Drug-resistant seizures have been defined by the International League Against Epilepsy (ILAE) as "failure of adequate trials of 2 tolerated and appropriately chosen and used AED schedules to achieve sustained seizure freedom" (Kwan et al, 2010). Furthermore, current AEDs possess undesirable toxicity for many patients; therefore, there remains a clear medical need for the development of improved anti-epileptic therapies that are more efficacious, easy to use, and better tolerated than those already on the market.

Benzodiazepines are nonselective PAMs of GABAA receptors with widespread utility in neurology and psychiatry, but their use is limited by sedation, psychomotor impairment, and other adverse effects. In the treatment of epilepsy, chronic use of BZDs can result in loss of efficacy, which precludes its use in many epilepsy populations.

CVL-865 is a novel, brain-penetrable, small molecule partial PAM of  $\alpha 2$ ,  $\alpha 3$ , and  $\alpha 5$  subunit containing GABAA receptors, with minimal functional activity at  $\alpha 1$  subunitcontaining receptors, which are believed to mediate many adverse effects observed with BZDs. By reducing the  $\alpha 1$  activity, CVL-865 has the potential to retain highly effective anticonvulsant activity, without the BZD-associated adverse effects.

CVL-865 has been shown to be anticonvulsant in several nonclinical models of epilepsy including the pentylenetrazol model in mice, the amygdala kindling model of temporal

lobe epilepsy in rats, and in the genetic absence epilepsy rat from Strasbourg. The strong efficacy across a broad spectrum of models is suggestive of potential clinical utility of CVL-865 in epilepsy.

Clinically, the first investigation of the anticonvulsant potential of CVL-865 was demonstrated in a Phase 2 photosensitive epilepsy model trial (Gurrell et al, 2019). In this proof-of-principle trial, photosensitive subjects were exposed to intermittent photic stimulation and the reduction in sensitivity was measured. CVL-865 showed robust suppression of the generalized photoparoxysmal electroencephalogram (EEG) response, following single doses of 17.5 and 52.5 mg, raising the possibility that CVL-865 may have potential efficacy in other epilepsy populations.

Currently, approximately 290 subjects have been administered CVL-865 in doses ranging from 0.04 to 100 mg single dose, and 2.5 mg to 42.5 mg twice daily (BID) multiple dose. CVL-865 has been safe and well tolerated.

Please refer to the Investigator's Brochure for a summary of available nonclinical and clinical safety data for CVL-865.

## 2.3 Benefit/Risk Assessment

There are no important identified risks for CVL-865. Fetal toxicity, bone marrow suppression and decrease in peripheral hematologic parameters are important potential risks; however, these risks will be minimized during the study by monitoring of hematologic parameters and requiring the use of appropriate contraception and regular pregnancy testing.

Results from a recently completed Phase 2a trial using a photosensitivity model as a proof-of-concept for CVL-865 demonstrated highly robust efficacy. This was shown by a marked and statistically significant mean reduction in standardized photosensitivity ranges to intermittent photic stimulations for single doses of 17.5 mg and 52.5 mg CVL-865 compared with placebo, which was similar to lorazepam 2 mg active control.

Based on available safety and efficacy data for CVL-865, the benefit-risk profile is favorable.

In response to the COVID-19 pandemic, Cerevel has performed a risk assessment of this trial and the investigator of each individual trial site and has implemented measures throughout the protocol, which prioritizes trial participant safety and data validity.

# **3 OBJECTIVES AND ENDPOINTS**

## Table 3 Objectives and Endpoints

Objectives	Endpoints
Primary: To evaluate the efficacy of CVL-865 as adjunctive therapy compared with placebo in subjects with focal onset seizures	Primary Efficacy: RRatio, defined as RRatio= $(T-B)/(T+B) \times 100$ , where T represents the focal onset seizure frequency rate per week in the Maintenance Phase and B represents the focal onset seizure frequency rate per week in the Baseline Period
	Key Secondary Efficacy:
	
 
Change from baseline in focal onset seizure frequency per week over the Maintenance Phase
 

	• The 50% responder rate, defined as the percent of subjects with at least a 50% reduction in the Maintenance Phase focal onset seizure frequency rate relative to the Baseline Period
	Other Secondary Efficacy:
	Seizure freedom
	Seizure rate over time
	• PGIC score at visits 2, 3, and 4
	• Change from Baseline to Visits 2, 3, and 4 in CGI-S score
	• CGI-I score at Visit 2, 3, and 4
	
 
Change from Baseline to Visit 4 in QOLIE-31 Overall score
 

	
 
Change from Baseline to Visit 4 in HUI Utility score
 

Secondary (safety): To evaluate the safety and tolerability of CVL-865 in subjects with focal onset seizures	• Treatment-emergent adverse events, clinically significant changes in ECGs, vital sign measurements, and physical and neurological examination results
	Suicidality assessed using the C-SSRS
	
 
Withdrawal symptoms assessed using the mCIWA-B
 

	
 
Nature, frequency, and temporality of TEAEs (nonserious and serious), including abuse-related AEs and AEs related to Medication Handling Irregularities (MHI)
 

Secondary (PK): To evaluate the plasma exposure of CVL-865	Summary listing of CVL-865     concentrations by dose and visit

Abbreviations: AE = adverse event; CGI-I = Clinical Global Impression – Improvement; CGI-S = Clinical Global Impression – Severity of Symptoms; C-SSRS = Columbia-Suicide Severity Rating Scale; ECG = electrocardiogram; HUI = Health Utilities Index; mCIWA-B = Modified Clinical Institute Withdrawal Assessment – Benzodiazepines; MHI = Medication Handling Irregularities; PGIC = Patient's Global

Impression of Change; QOLIE-31 = Quality of Life in Epilepsy-31; RRatio = Response Ratio; TEAE = treatment-emergent adverse event.

## 4 TRIAL DESIGN

## 4.1 Overall Design

This is a double-blind, parallel-group, placebo-controlled trial with subjects randomized to 1 of the following 3 arms in a 1:1:1 ratio:

- CVL-865 25 mg BID maintenance
- CVL-865 7.5 mg BID maintenance
- Placebo

This trial is designed with a maximum duration of approximately 25 weeks. The trial consists of the following:

- 8-week Screening/Baseline Period
- 10- or 13-week Treatment Period, including an initial 2-week Titration Phase, an 8-week Maintenance Phase, and a 3-week Taper Phase (only for subjects not continuing treatment in the open-label extension trial). The tablets (including the number of tablets given) will be the same between the placebo and both CVL-865 dose arms during the Titration, Maintenance, and Taper Phases to maintain the blind
- 4-week Follow-up Period

#### Screening/Baseline Period:

Only subjects who have signed an informed consent form (ICF) and are expected to fulfill the inclusion/exclusion criteria enter into the Screening/Baseline Period for evaluation at the Screening Visit. Subjects are to continue on their current AEDs at the same dosages throughout the Screening/Baseline Period. If a subject has a vagus nerve stimulator (VNS), a deep brain stimulator (DBS), or a responsive neurostimulator (RNS), the settings must remain stable throughout the Screening/Baseline Period.

During this Screening/Baseline Period, subjects will be required to complete electronic seizure diaries (eDiary) and record all seizures in the eDiary for each day. The presence or absence of all seizure types experienced by each subject will be recorded daily in the eDiary.

#### Treatment Period:

Subjects who satisfy all inclusion/exclusion criteria and thus are eligible for the trial will be randomized to 1 of 3 treatment arms at Visit 1.

The daily dosing schedule will start at Day 1 with a 2-week Titration Phase during which time the subject's dose will be increased in a blinded fashion up the randomized dose level (CVL-865 25 mg BID, CVL-865 7.5 mg BID, or placebo). In the high-dose group, CVL-865 will be administered as

during the Titration Phase, and then 25 mg BID during the 8-week Maintenance Phase. In the low-dose group, CVL-865 will be administered as

during the Titration Phase, and then 7.5 mg BID

during the 8-week Maintenance Phase.

At the completion of the Maintenance Phase, the investigator will evaluate the subject's eligibility to continue treatment with CVL-865 in the open-label extension trial CVL-865-SZ-002. If the investigator determines the subject is eligible for the trial, he/she will discuss with the subject if they would like to continue into Trial CVL-865-SZ-002. If the investigator determines the subject is eligible and the subject agrees to continue participation in Trial CVL-865-SZ-002, consent will be obtained and unique procedures for Visit 1 of Trial CVL-865-SZ-002 will be completed.

For subjects who do not continue into Trial CVL-865-SZ-002, following the Maintenance Phase, the dose will be gradually decreased over a 3-week Taper Phase.

A summary of the dosing schedule is provided below.

	Titratio	on Phase	Maintenance Phase	Taper Phase a				
Dose Initiation			Day 15	Day 78	Day 85	Day 92		
Duration	2 w	eeks	8 weeks					
CVL-865 7.5 mg BID			7.5 mg BID	5 mg BID	5 mg BID	2.5 mg BID		
CVL-865 25 mg BID			25 mg BID	17.5 mg BID	10 mg BID	5 mg BID		
Placebo	Placebo	Placebo	Placebo	Placebo	Placebo	Placebo		

Table 4 Dosing Schedule

Abbreviations: BID = twice daily.

a Only for subjects who do not continue treatment with CVL-865 in Trial CVL-865-SZ-002.

Subjects are to continue the same concurrent AEDs at the same dosages administered during the Treatment Period. If a subject has a VNS, DBS, or RNS, the settings must remain stable throughout the Treatment Period.

Subjects will continue to record all seizures and the presence or absence of all seizure types experienced in the eDiary for each day during the Treatment Period.

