AED = anti-epileptic drug; BID = twice daily; BZD = benzodiazepine; CGI-I = Clinical Global Impression-Improvement; CGI-S = Clinical Global Impression – Severity of Symptoms; C-SSRS = Columbia-Suicide Severity Rating Scale; CT = computed tomography; ECG = electrocardiogram; ET = Early Termination; HBV = hepatitis B virus; HCG = human chorionic gonadotropin; HCV = hepatitis C virus; HIV = human immunodeficiency virus; ICF = informed consent form; IMP = investigational medicinal product; mCIWA-B = Modified Clinical Institute Withdrawal Assessment – Benzodiazepines; MRI = magnetic resonance imaging; PGIC = Patient Global Impression of Change; PK = pharmacokinetic; QOLIE-31 = Quality of Life in Epilepsy-31; SIF/DRF = Seizure Identification and Diagnostic Review Form; TESC = The Epilepsy Study Consortium.

- a. Individual sites may require subjects to have COVID-19 testing done prior to randomization. COVID-19 testing may be performed after randomization per the investigator's discretion.
- b. Contact with subject via phone call or other means of communication to check on their status.
- c. In the event that a subject is unable to attend a clinic visit in person due to restrictions related to COVID-19, this visit may be completed remotely. Please refer to the Trial Operations Manual for further instructions related to remote visits.
- d. At Visit 4, the investigator will evaluate the subject's eligibility to continue treatment with CVL-865 in the open-label extension trial CVL-865-SZ-002. If the investigator determines the subject is eligible for the trial, he/she will discuss with the subject if they would like to continue into Trial CVL-865-SZ-002. If the investigator determines the subject is eligible and the subject agrees to continue participation in Trial CVL-865-SZ-002, consent will be obtained and unique procedures for Visit 1 of Trial CVL-865-SZ-002 will be completed. Subjects who do not continue into Trial CVL-865-SZ-002 will begin the Taper Phase.

- e. Subjects who require early termination should begin the Taper Period at the time the decision is made to discontinue. All indicated procedures should be performed per protocol. If a subject discontinues early and it is inadvisable for them to taper IMP (after agreement from medical monitor), the subject should complete Visit 6 assessments approximately 30 days following the last dose of IMP.

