## 4.4 Definition of Completed Subject

Subjects continuing treatment with CVL-865-SZ-001 in the open-label extension trial are considered to have completed this trial if he/she has completed the Maintenance Phase of the trial (ie, completed Visit 4) as shown in the Schedule of Assessments.

Subjects not continuing in the open-label extension trial, are considered to have completed this trial if he/she has completed all phases of the trial including the last scheduled procedure (Day 120 phone contact) shown in the Schedule of Assessments.

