1.4. Treatment Period

The dose of CVL-865 will be titrated to the assigned dose over the first 2 weeks of the trial during the Dose Titration Phases followed by 8 weeks of Maintenance Phase at the assigned dose level. At the end of Maintenance Phase, eligible subjects have the option to continue treatment with CVL-865 in the open-label extension trial CVL-865-SZ-002. If for subjects who do not continue into Trial CVL-865-SZ-002, following the Maintenance Phase, the dose will be gradually decreased over a 3-week Taper Phase.

The dosing schedule is summarized in Table 1.

Table 1:	Dosing Schedule
----------	-----------------

	Titratio	n Phase	Maintenance Phase		Taper Pha	ise ^a
Dose Initiation			Day 15	Day 78	Day 85	Day 92
Duration	2 weeks		8 weeks		3 weeks	
CVL-865 7.5 mg BID			7.5 mg BID	5 mg BID	5 mg BID	2.5 mg BID
CVL-865 25 mg BID			25 mg BID	17.5 mg BID	10 mg BID	5 mg BID
Placebo	Placebo	Placebo	Placebo	Placebo	Placebo	Placebo

Abbreviations: BID = twice daily.

^a Only for subjects who do not continue treatment with CVL-865 in Trial CVL-865-SZ-002.

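### The dosing tables in both documents start each taper step 7 days later than the stated phase durations and the Visit 4 (Day 71) taper start allow

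*Protocol*

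**What the plan says.** Protocol Table 4 (section 4.1, Treatment Period) has a row labelled 'Dose Initiation'. Its legible entries are "Day 15 Day 78 Day 85 Day 92": one for Maintenance, then one for each of the three taper steps. SAP Table 1 (section 1.4) repeats the same taper days, "Day 78 Day 85 Day 92", and prints 8 weeks for Maintenance and 3 weeks for the taper beneath them.

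Other places in the two documents set the timing differently:

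- Protocol 4.1 gives the durations as "10- or 13-week Treatment Period, including an initial 2-week Titration Phase, an 8-week Maintenance Phase, and a 3-week Taper Phase", inside a "maximum duration of approximately 25 weeks".
- The text above Table 4 runs the taper straight on from Maintenance: "following the Maintenance Phase, the dose will be gradually decreased over a 3-week Taper Phase". SAP 1.4 says the same.
- Protocol Table 2 footnote d, attached to Visit 4 (Day 71), says "Subjects who do not continue into Trial CVL-865-SZ-002 will begin the Taper Phase".
- Protocol 4.4 treats completing Visit 4 as completing Maintenance.
- SAP Table 3 ends Maintenance the day before Visit 4 and starts the Taper Phase on Day 71.
- Protocol Table 2 places Days 78, 85 and 92 inside the 3-week Taper Phase as two contacts and Visit 5, and places the contact at about Day 99 in follow-up. IMP is dispensed at Visits 1 to 4 only, and IMP compliance is last assessed at Visit 5 or early termination.

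**The concern.** In the visible text this row is the only place that dates the individual taper steps, and it is a dosing instruction for withdrawing a GABA-A modulator from people with drug-resistant epilepsy. A site that follows the row keeps the subject on the maintenance dose for a further week after Visit 4. A site that follows footnote d steps the dose down at Visit 4. The row also starts the lowest step at Visit 5, where no IMP is dispensed and after which no IMP compliance is assessed.

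Withdrawal symptoms on the mCIWA-B are a secondary safety endpoint. SAP 5.14.8 measures change from the last on-treatment assessment on or before Day 71. If the row is followed, the Day 78 score comes after another week at full dose, although the schedule treats it as the first assessment of the taper.

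**Working it through.** **Inputs.** First dose on Day 1; titration 2 weeks, Maintenance 8 weeks, taper 3 weeks, follow-up 4 weeks (Protocol 4.1). Visit 4 is Day 71, Visit 5 is Day 92 and Visit 6 is Day 120 (Protocol Table 2). Taper steps are 17.5, 10 and 5 mg BID in the 25 mg BID arm and 5, 5 and 2.5 mg BID in the 7.5 mg BID arm (Protocol Table 4).

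**What reproduces.**
- Maintenance start: 1 + 14 = Day 15, as printed.
- Treatment Period: 2 + 8 + 3 = 13 weeks. Whole trial: 8 + 13 + 4 = 25 weeks, as stated.
- Follow-up: 120 − 92 = 28 days = 4 weeks, as stated.

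**What does not reproduce.**
- Last day of Maintenance: 15 + 56 − 1 = Day 70, so the first taper step starts on Day 71.
- Weekly steps then start on Days 71, 78 and 85, and 71 + 21 = Day 92 is Visit 5.
- Printed minus derived: 78 − 71, 85 − 78 and 92 − 85, each 7 days. The ±3-day visit window cannot absorb this.

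**The row read literally.**
- Maintenance is Days 15–77: 78 − 15 = 63 days = 9 weeks, against the 8 weeks printed in the same table.
- If the last step lasts 7 days: 92 + 6 = Day 98, so treatment lasts 98/7 = 14 weeks and 120 − 98 = 22 days remain to Visit 6.
- If the taper stops at Visit 5 instead: 92 − 78 = 14 days, which is 2 weeks of taper and not 3.

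No literal reading satisfies all the stated durations.

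**Dose on Days 71–77.**
- 25 mg BID arm: 2 × 25 = 50 mg/day if Maintenance continues, 2 × 17.5 = 35 mg/day if the first step has begun. The difference is 15 mg/day.
- 7.5 mg BID arm: 2 × 7.5 = 15 mg/day against 2 × 5 = 10 mg/day. The difference is 5 mg/day.

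**Dose in the week before each scheduled mCIWA-B assessment** (the literal Day 99 entry assumes a 7-day last step):

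| Assessment | 25 mg BID arm: steps from Day 71 | 25 mg BID arm: printed row | 7.5 mg BID arm: steps from Day 71 | 7.5 mg BID arm: printed row |
|---|---|---|---|---|
| Day 78 | 17.5 mg BID | 25 mg BID | 5 mg BID | 7.5 mg BID |
| Day 85 | 10 mg BID | 17.5 mg BID | 5 mg BID | 5 mg BID |
| Day 92 | 5 mg BID | 10 mg BID | 2.5 mg BID | 5 mg BID |
| About Day 99 | none | 5 mg BID | none | 2.5 mg BID |

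**The case against.** The best defence is that Days 78, 85 and 92 are the taper contacts and Visit 5, so the row probably shows the day each step ends under a label meant for starts. That reading fits every stated duration and is the likely origin of the figures. It does not rescue the row: the label says initiation, and Day 15 in the same row is a true start day. Redaction is not the cause either, because the blacked-out titration cells play no part and the same days are legible in both documents.

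The objections to the consequences are stronger, and most of them stand. Several other passages point to Day 71. Neither reading takes a subject above a dose already being taken, and Protocol 4.3 reports multiple doses up to 42.5 mg BID as well tolerated in healthy adults. Protocol 6.4 has the time and dose of actual administrations recorded. What sites and subjects follow in practice may be the blister packs, the manuals or Figure 1, none of which can be seen.

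A reader might also infer effects that the documents do not support:

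- **Distorted compliance percentages.** SAP 4.1.10 compares the number of doses taken with the number expected over the same period, and SAP Table 3 ends the Taper Phase at end of treatment. Nothing extends the expected count to Day 98, and a count of doses does not change when only the strength on a given day changes.
- **Distorted average-dose or dose-at-onset summaries.** SAP 4.1.9 works from doses recorded in the eCRF and the periods in SAP Table 3, not from the dosing table. Dose at event onset can come from the same records.
- **A longer Maintenance window for efficacy.** SAP Table 3 ends that window the day before Visit 4.

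**Conclusion.** The inconsistency is real. In both dosing tables every taper step is labelled as starting 7 days later than the stated durations, footnote d, Protocol 4.4 and SAP Table 3 allow. It should be fixed because it is a dosing instruction, but it does not threaten the validity of the trial.

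Its reach is limited to subjects who complete Visit 4 and do not enter the extension; the documents do not give their number. Early terminators are outside it, because Protocol Table 2 footnote e starts their taper when the decision to discontinue is made. For the affected subjects two things are ambiguous: the dose on Days 71–77 (a difference of 15 or 5 mg/day, by arm) and the timing of the mCIWA-B assessments relative to the dose steps. The Day 98 end, the 14 weeks of treatment and the 22 days to Visit 6 all assume a 7-day last step. The primary and key secondary endpoints are unaffected.

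It is tempting to conclude that subjects were tapered wrongly. The visible text cannot show that, and it does not show which schedule sites used.

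**What to change.** In Protocol Table 4 and SAP Table 1, change the three taper 'Dose Initiation' days to Day 71 (Visit 4), Day 78 and Day 85, with the taper ending at Visit 5 (Day 92).

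Have the sponsor state the last taper dose, either the evening of Day 91 or the morning of Day 92. The choice should agree with Protocol Table 2 footnote q, which records a same-day morning IMP dose with the PK sample at Visits 2 to 5. If the evening of Day 91 is chosen, footnote q needs a matching change for Visit 5. The documents do not settle this.

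Send sites a short clarification. The cost is one table row in each document and that notice, with no new visits, procedures or data. The protocol row may need an amendment with IRB/IEC approval (Protocol 10.1.1). If dosing has already finished, the site notice falls away, and the SAP row should still be corrected before database lock.

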## Follow-up Period:

See Figure 1 for a schematic of the trial design and Table 2 for the schedule of assessments.

## 4.2 Scientific Rationale for Trial Design

CVL-865 is a novel small molecule with a first-in-class mechanism of action, which, based on the nonclinical and clinical data, has the potential to be highly efficacious in a broad spectrum of patients with epilepsy via modulation of GABAA receptors. As an  $\alpha 2/\alpha 3/\alpha 5$  subtype selective partial PAM with minimal effect at the  $\alpha 1$  subunit, CVL-865 would be expected to maintain efficacy whilst overcoming many of the adverse events (AEs) that limit the use of BZDs, such as cognitive impairment, sedation, withdrawal symptoms, abuse potential, and tolerance.

The clinical development of anti-epileptic agents in focal onset epilepsy in the adjunctive setting is well established. Usually, focal seizures in adults represent the first patient population, since they are the most frequent seizure type, and a substantial percentage of patients have seizures that are not well controlled using current medications. The initial evaluation process for a new AED involves determination of its efficacy in reducing the frequency of seizures in patients who continue to have seizures despite therapy with an adequate dosage of appropriate drug(s) and thus represent a drug-resistant population.

This trial includes a randomized, double-blind, placebo-controlled parallel group design, which are the key features recommended by the European Medicines Agency draft guidelines 2018 on the clinical investigation of medicinal products in the treatment of epileptic disorders (EMA 2018).

